6.1 Treatment Administration

- 6.1.1 Treatment will be administered on an *inpatient or outpatient* basis based on the type of medication selected. The physician will administer the drug as directed in the FDA approved label.
- 6.1.2 If the drug is approved with different doses or schedules for different cancers, it will be administered according to the indication for the organ system matching that of the patient (if available). If not available, the drug will be administered at a dose as indicated by the organ system most closely related to the patient's primary disease. The cycling will be determined as directed in Section 6.2.1.
- 6.1.3 Reported adverse events and potential risks are described in the label and will be communicated to the patient at the time of drug selection.

Appropriate dose modifications for the drugs are described in the FDA label and made at the treating physician's discretion.

6.1.4 Investigational agent

The investigational agent in this protocol will be an FDA approved targeted therapy that target specific mutations in specific disease.

Supportive care regimens will vary depending on the type of drug that will be administered at the treating physician's discretion.

6.2 General Concomitant Medication and Supportive Care Guidelines

Patients should receive *full supportive care*, including transfusions of blood and blood products, erythropoietin, antibiotics, antiemetics, etc., as clinically indicated. Anti-inflammatory or narcotic analgesics may be offered as needed. Medications considered necessary for the patient's well-being may be given at the discretion of the investigator, i.e., chronic treatments for concomitant medical conditions, as well as agents required for life-threatening medical problems, etc. The reason(s) for treatment, dosage, and dates of treatment should be recorded in the medical record.

6.3 Duration of Therapy

In the absence of treatment delays due to adverse events, treatment may continue for the number of cycles indicated on the FDA label, or until one of the following criteria applies:

- Disease progression,
- Intercurrent illness that prevents further administration of treatment,
- Unacceptable adverse event(s),
- Patient decides to withdraw from the study, or

- General or specific changes in the patient's condition render the patient unacceptable for further treatment in the judgment of the investigator.

6.4 Duration of Follow Up

Patients will be followed for adverse events a minimum of 30 days after date of last study drug administration, unless otherwise specified in this section of the protocol. Follow-up for serious adverse events and mortality after the last study drug dose is administered will take place during the routine clinic visits that the patient will have during the 30-day follow-up window (Also referenced in Appendix D). If no visit occurs during this window, a phone call confirmation should be made to the patient to determine vital status and whether any adverse events and in particular, Grade 4 unexpected adverse events occurred during that window of time and recorded on Appendix F.

If a patient is removed from the study, patients will be followed for 30 days after removal from study for adverse events. Patients removed from study for unacceptable adverse events will be followed until resolution or stabilization of the adverse event.

Patients will be followed until death for monitoring survival study endpoints.

6.5 Criteria for Removal from Study

Patient refusal to continue on study or unable/unwilling to comply with study procedures.

7.0 Dosing Delays/Dose Modifications

As this protocol will use multiple chemotherapeutic agents Dosing delays and modifications will be made as indicated in the FDA label of the drug unless indicated differently by the treating physician.

8.0 Measurement of Effect

The response criteria will vary based on the type of cancer being treated. A cache of response forms is in Appendix (TBD).

8.1 Antitumor Effect – Solid Tumors

Response and progression will be evaluated in this study using the Response Evaluation Criteria in Solid Tumors (RECIST) criteria 1.1.(Eisenhauer et al., 2009) Changes in the largest diameter (unidimensional measurement) of the tumor lesions and the shortest diameter in the case of malignant lymph nodes are used in the RECIST criteria. For diseases where RECIST is not employed, response will be measured in accordance with the measurement instrument used for

that specific disease. The specific measurement Criteria being used will be recorded prior to treatment

8.1.1 Definitions

- **Evaluable for toxicity:**

All patients will be evaluable for toxicity from the time of their first treatment with the study treatment of interest.

- **Evaluable for objective response:**

Only those patients who have measurable disease present at baseline, have received at least one cycle of therapy, and have had their disease re-evaluated will be considered evaluable for response. These patients will have their response classified according to the definitions stated below. (Note: Patients who exhibit objective disease progression prior to the end of cycle 1 will also be considered evaluable.)

- **Evaluable Non-Target Disease Response.**

Patients who have lesions present at baseline that are evaluable but do not meet the definitions of measurable disease, have received at least one cycle of therapy, and have had their disease re-evaluated will be considered evaluable for non-target disease. The response assessment is based on the presence, absence, or unequivocal progression of the lesions.

- **Measurable disease / measurable lesions**

Measurable lesions are defined as those that can be accurately measured in at least one dimension (longest diameter to be recorded) as ≥ 20 mm by chest x-ray, as ≥ 10 mm with CT scan, or ≥ 10 mm with calipers by clinical exam. All tumor measurements must be recorded in millimeters (or decimal fractions of centimeters).

- **Malignant lymph nodes.**

To be considered pathologically enlarged and measurable, a lymph node must be ≥ 15 mm in short axis when assessed by CT scan (CT scan slice thickness recommended to be no greater than 5 mm). At baseline and in follow-up, only the short axis will be measured and followed.

- **Non-measurable disease / non-measurable lesions:**

All other lesions (or sites of disease), including small lesions (longest diameter <10 mm or pathological lymph nodes with ≥ 10 to <15 mm short axis), are considered non-measurable disease. Bone lesions, leptomeningeal disease, ascites, pleural/pericardial effusions, lymphangitis cutis/pulmonitis, inflammatory breast disease, and abdominal masses (not followed by CT or MRI), are considered as non-measurable.

Note: Cystic lesions that meet the criteria for radiographically defined simple cysts should not be considered as malignant lesions (neither measurable nor non-measurable) since they are, by definition, simple cysts.

'Cystic lesions' thought to represent cystic metastases can be considered as measurable lesions, if they meet the definition of measurability described above. However, if non-cystic lesions are present in the same patient, these are preferred for selection as target lesions.

- **Target lesions**

All measurable lesions up to a maximum of 2 lesions per organ and 5 lesions in total, representative of all involved organs, should be identified as **target lesions** and recorded and measured at baseline. Target lesions should be selected on the basis of their size (lesions with the longest diameter), be representative of all involved organs, but in addition should be those that lend themselves to reproducible repeated measurements. It may be the case that, on occasion, the largest lesion does not lend itself to reproducible measurement in which circumstance the next largest lesion which can be measured reproducibly should be selected. A sum of the diameters (longest for non-nodal lesions, short axis for nodal lesions) for all target lesions will be calculated and reported as the baseline sum diameters. If lymph nodes are to be included in the sum, then only the short axis is added into the sum. The baseline sum diameters will be used as reference to further characterize any objective tumor regression in the measurable dimension of the disease.

- **Non-target lesions**

All other lesions (or sites of disease) including any measurable lesions over and above the 5 target lesions should be identified as **non-target lesions** and should also be recorded at baseline. Measurements of these lesions are not required, but the presence, absence, or in rare cases unequivocal progression of each should be noted throughout follow-up.

8.1.2 Methods for Evaluation of Measurable Disease

- **Method(s) for obtaining measurements:**

All measurements should be taken and recorded in metric notation using a ruler or calipers. All baseline evaluations should be performed as closely as possible to the beginning of treatment and never more than 4 weeks before the beginning of the treatment.

The same method of assessment and the same technique should be used to characterize each identified and reported lesion at baseline and during follow-up. Imaging-based evaluation is preferred to evaluation by clinical examination unless the lesion(s) being followed cannot be imaged but are assessable by clinical exam.

Clinical lesions: Clinical lesions will only be considered measurable when they are superficial (e.g., skin nodules and palpable lymph nodes) and ≥ 10 mm diameter as assessed using calipers (e.g., skin nodules). In the case of skin lesions, documentation by color photography, including a ruler to estimate the size of the lesion, is recommended.

- **Time frame for obtaining measurements**

Patients will undergo imaging every two cycles of therapy ± 10 days until progression. In the event that patient discontinues treatment for reasons other than progression, imaging shall continue until progression on the same schedule employed while the patient was receiving treatment

- **Use of imaging techniques (e.g., x-ray, CT, MRI, PET) for measuring disease**

Chest x-ray: Lesions on chest x-ray are acceptable as measurable lesions when they are clearly defined and surrounded by aerated lung. However, CT is preferable.

Conventional CT and MRI: This guideline has defined measurability of lesions on CT scan based on the assumption that CT slice thickness is 5 mm or less. If CT scans have slice

thickness greater than 5 mm, the minimum size for a measurable lesion should be twice the slice thickness. MRI is also acceptable in certain situations (e.g. for body scans).

Use of MRI remains a complex issue. MRI has excellent contrast, spatial, and temporal resolution; however, there are many image acquisition variables involved in MRI, which greatly impact image quality, lesion conspicuity, and measurement. Furthermore, the availability of MRI is variable globally. As with CT, if an MRI is performed, the technical specifications of the scanning sequences used should be optimized for the evaluation of the type and site of disease. Furthermore, as with CT, the modality used at follow-up should be the same as was used at baseline and the lesions should be measured/assessed on the same pulse sequence. It is beyond the scope of the RECIST guidelines to prescribe specific MRI pulse sequence parameters for all scanners, body parts, and diseases. Ideally, the same type of scanner should be used and the image acquisition protocol should be followed as closely as possible to prior scans. Body scans should be performed with breath-hold scanning techniques, if possible.

PET-CT: At present, the low dose or attenuation correction CT portion of a combined PET-CT is not always of optimal diagnostic CT quality for use with RECIST measurements. However, the CT portion of the PET-CT may be used for RECIST measurements at baseline Note, however, that the PET portion of the CT introduces additional data which may bias an investigator if it is not routinely or serially performed.

Ultrasound: Ultrasound is not useful in assessment of lesion size and should not be used as a method of measurement. Ultrasound examinations cannot be reproduced in their entirety for independent review at a later date and, because they are operator dependent, it cannot be guaranteed that the same technique and measurements will be taken from one assessment to the next. If new lesions are identified by ultrasound in the course of the study, confirmation by CT or MRI is advised. If there is concern about radiation exposure at CT, MRI may be used instead of CT in selected instances.

Endoscopy, Laparoscopy: The utilization of these techniques for objective tumor evaluation is not advised. However, such techniques may be useful to confirm complete pathological response when biopsies are obtained or to determine relapse in trials where recurrence following complete response (CR) or surgical resection is an endpoint.

FDG-PET: While FDG-PET response assessments need additional study, it is sometimes reasonable to incorporate the use of FDG-PET scanning to complement CT scanning in assessment of progression (particularly possible 'new' disease). New lesions on the basis of FDG-PET imaging can be identified according to the following algorithm:

- a. Negative FDG-PET at baseline, with a positive FDG-PET at follow-up is a sign of PD based on a new lesion.
- b. No FDG-PET at baseline and a positive FDG-PET at follow-up: If the positive FDG-PET at follow-up corresponds to a new site of disease confirmed by CT, this is PD. If the positive FDG-PET at follow-up is not confirmed as a new site of disease on CT, additional follow-up CT scans are needed to determine if there is truly progression occurring at that site (if so, the date of PD will be the date of the initial abnormal FDG-PET scan). If the positive FDG-PET at follow-up corresponds to a pre-existing site of disease on CT that is not progressing on the basis of the anatomic images, this is not PD.

- c. FDG-PET may be used to upgrade a response to a CR in a manner similar to a biopsy in cases where a residual radiographic abnormality is thought to represent fibrosis or scarring. The use of FDG-PET in this circumstance should be prospectively described in the protocol and supported by disease-specific medical literature for the indication. However, it must be acknowledged that both approaches may lead to false positive CR due to limitations of FDG-PET and biopsy resolution/sensitivity.

Note: A 'positive' FDG-PET scan lesion means one which is FDG avid with an uptake greater than twice that of the surrounding tissue on the attenuation corrected image.

- **How tumor markers will be measured and assessed, if applicable**

Tumor markers: Tumor markers alone cannot be used to assess response. If markers are initially above the upper normal limit, they must normalize for a patient to be considered in complete clinical response. Specific guidelines for both CA-125 response (in recurrent ovarian cancer) and PSA response (in recurrent prostate cancer) have been published [JNCI 96:487-488, 2004; J Clin Oncol 17, 3461-3467, 1999; J Clin Oncol 26:1148-1159, 2008]. In addition, the Gynecologic Cancer Intergroup has developed CA-125 progression criteria which are to be integrated with objective tumor assessment for use in first-line trials in ovarian cancer [JNCI 92:1534-1535, 2000].

- **Use of cytology or histology for assessment, if applicable**

Cytology, Histology: These techniques can be used to differentiate between partial responses (PR) and complete responses (CR) in rare cases (e.g., residual lesions in tumor types, such as germ cell tumors, where known residual benign tumors can remain).

8.1.3 Response Criteria

- **Definition of complete response (CR)** for target and non-target lesions, as appropriate

- Target Lesions:
 - Disappearance of all target lesions and normalization of tumor marker level. **Any pathological lymph nodes (whether target or non-target) must have reduction in short axis to <10 mm** (the sum may not be "0" if there are target nodes)
 - Note: If tumor markers are initially above the upper normal limit, they must normalize for a patient to be considered in complete clinical response.
- Non-target lesions:
 - Disappearance of all non-target lesions and normalization of tumor marker level. **All lymph nodes must be non-pathological in size (< 10 mm short axis)**

- **Definition of partial response (PR)** for target and non-target lesions, as appropriate

- Target lesions:
 - At least a 30% decrease in the sum of diameters of target lesions, taking as reference the baseline sum of diameters
- Non-target lesions

- **Non-CR/Non-PD:** Persistence of 1 or more **non-target lesion(s)** and/or maintenance of tumor marker level above the normal limits
- **Definition of progressive disease (PD)** for target and non-target lesions, as appropriate
 - Target Lesions:
 - > 20% increase in the SLD taking as reference the smallest SLD recorded since the treatment started (nadir) **and minimum 5 mm increase over the nadir**
 - When sum becomes very small, increases within measurement error (2-3 mm) can lead to 20% increase
 - (Note: the appearance of one or more new lesions is also considered progressions)
 - Non-target lesions:
 - *Unequivocal progression* of existing non-target lesions. The appearance of one or more new lesions.
 - *Unequivocal progression* should not normally trump target lesion status. It must be representative of overall disease status change, not a single lesion increase
 - Although a clear progression of “non-target” lesions only is exceptional, the opinion of the treating physician should prevail in such circumstances, and the progression status should be confirmed at a later time by the review panel (or Principal Investigator).
- **Definition of stable disease (SD)** for target and non-target lesions, as appropriate
 - Target lesions:
 - Neither sufficient shrinkage to qualify for PR nor sufficient increase to qualify for PD, taking as reference the smallest sum diameters while on study
- **Definition and evaluation of best overall response**, if applicable
The best overall response is the best response recorded from the start of the treatment until disease progression/recurrence (taking as reference for progressive disease the smallest measurements recorded since the treatment started). The patient's best response assignment will depend on the achievement of both measurement and confirmation criteria.

Best Overall Response Table When Confirmation of CR or PR is required

Overall Response First Timepoint	Overall Response Subsequent Timepoint	BEST overall response
CR	CR	CR
CR	PR	SD, PD, OR PR
CR	SD	SD provided minimum criteria for SD duration are met. Otherwise PD
CR	PD	SD provided minimum criteria for SD duration are met. Otherwise PD

Precision medicine for patients with identified actionable mutations at Wake Forest Baptist Comprehensive Cancer Center (WFBCCC): A pragmatic trial
WFBCCC # 04519

CR	NE	SD provided minimum criteria for SD duration are met. Otherwise NE
PR	CR	PR
PR	PR	PR
PR	SD	SD
PR	PD	SD provided minimum criteria for SD duration are met. Otherwise PD
PR	NE	SD provided minimum criteria for SD duration are met. Otherwise NE
NE	NE	NE

Overall Response Table for Patients with Measurable Disease

Target Lesions	Non-Target Lesions	New Lesions	Overall Response	Best Response for this Category Also Requires:
CR	CR	No	CR	≥ 4 wks. confirmation
CR	Non-CR/Non-PD	No	PR	≥ 4 wks. confirmation
CR	NE	No	PR	
PR	Non-PD or NE	No	PR	
SD	Non-PD or NE	No	SD	documented at least once ≥ 4 wks. from baseline
Not all evaluated	Non-PD	No	NE	
PD	Any	Yes or No	PD	no prior SD, PR or CR
Any	PD*	Yes or No	PD	
Any	Any	Yes	PD	

*In exceptional circumstances, unequivocal progression in non-target lesions may be accepted as disease progression.

Note: Patients with a global deterioration of health status requiring discontinuation of treatment without objective evidence of disease progression at that time should be reported as “*symptomatic deterioration*”. Every effort should be made to document the objective progression even after discontinuation of treatment.

Overall Response Table for Patients with Non-Measurable Disease (i.e., Non-Target Disease)

Non-Target Lesions	New Lesions	Overall Response
CR	No	CR
Non-CR/non-PD	No	Non-CR/non-PD*
Not all evaluated	No	not evaluated
Unequivocal PD	Yes or No	PD
Any	Yes	PD

* 'Non-CR/non-PD' is preferred over 'stable disease' for non-target disease since SD is increasingly used as an endpoint for assessment of efficacy in some trials so to assign this category when no lesions can be measured is not advised

8.1.4 Survival Outcomes

Progression-Free Survival is defined as the duration of time from the start of treatment to the time of progression, death, or date of last contact; those lost to follow-up will be censored.

Progression-Free Ratio is defined as the duration of time from start of treatment to the time of progression divided by the duration of time from the last treatment received pre-trial to the time of progression on that treatment. Those that die before progression or are lost to follow-up will be non-evaluable for the primary objective.(Cirkel et al., 2016)

Overall Survival is defined as the duration of time from the start of treatment to date of death or date of last contact; those lost to follow-up will be censored.

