5.2 Secondary Outcomes

- 5.2.1 Overall survival (OS), defined as the duration of time from the start of treatment to date of death or date of last contact; those lost to follow-up will be censored.
- 5.2.2 Investigational Agent Safety To determine incidence of adverse events (AEs), serious adverse events (SAEs), and any laboratory abnormalities of each investigational agent tested.
- 5.2.3 To measure response rate of treatment based on a simplified selection methodology using the NGS results.

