	Pre-Study ^a	Cycle 2, Day 1	Day 1; every even cycle (after cycle 2)	End of Treatment ±7 days	Follow up for Safety (30+ days after last treatment) required only if pt has treatment related AEs at end of treatment visit
Informed Consent	X				
Demographics	X				
Medical History	X				
Concurrent Meds	X				
Physical Exam	X	X	X	X	X
Vital Signs	X	X	X	X	X
Performance Status	X	X	X	X	X
Bone Marrow Biopsy ^h	X	X	X	X	
Imaging ^d	X	X	X ^f	X	
CBC w/diff, platelets ^e	X	X	X	X	X
Serum Chemistry ^b	X	X	X	X	X
B-HCG ^c	X				
Dose Adjustment Form		X	X		
Adverse Event Evaluation		X	X	X	X
Survival Status/Telephone Follow up ^g					X
PROMIS 29	X	X		X	
Satisfaction with Medical Decision Scale	X	X		X	
Patient Reported Outcome- Demographics/Health Literacy	X				

^a Pre-study requirements listed in table must be completed **within** 30 days prior to registration. Imaging demonstrating disease progression should be completed within 60 days of registration. Imaging should be repeated if the scan occurred more than 30 days prior to treatment initiation..

^b Albumin, alkaline phosphatase, total bilirubin, bicarbonate, BUN, calcium, chloride, creatinine, glucose, potassium, total protein, SGOT[AST], SGPT[ALT], sodium.

^c Serum pregnancy test within 10 days of Pre-study visit (women of childbearing potential only).

^d Imaging will be performed as part of SOC for solid tumors every other cycle, however due to patients on different drug treatment regimen, this may occur at 6 weeks ±2 weeks, 8 weeks ± 2 weeks or 12 weeks ± 2 weeks. Not required for leukemias. As clinically indicated in Multiple myeloma.

^e Labs will be performed in accordance with the recommendations of the prescribing instructions for the drug that is utilized

^f If treatment is discontinued for reasons other than progression, imaging will be performed on the same schedule as was utilized while patient was receiving treatment until progression.

^g Survival and information related to cancer treatment received after the study and disease status is monitored bimonthly via telephone contact or EMR review after treatment termination. Medical record review will be performed to coincide with the bimonthly telephone call to obtain information regarding evidence and of relapse (as documented on CT, PET, biopsy, etc).

^h If clinically indicated bone marrow biopsy will be repeated to evaluate response to therapy.

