14.3 Analysis of Secondary and Exploratory Objectives

Response rate will be estimated for all patients with corresponding 95% confidence intervals. Progression-free survival and overall survival times will be displayed using Kaplan-Meier curves with median survival times and confidence intervals. Adverse events will be summarized in incidence tables by type and grade severity for all patients and presented by type of treatment received. For exploratory objectives, the frequency of types of actionable mutations and previous treatment history will be summarized and demographic characteristics presented. Logistic models will be constructed for each type of mutation (yes/no) to preliminarily explore associations with clinical and demographic characteristics. For quality of life and patient satisfaction outcomes, changes over time will be assessed using a repeated measures ANOVA, with any between time associations utilizing Tukey adjustment for post-hoc comparisons. Transformations and/or non-parametric approaches will be considered for any outcomes violating parametric assumptions.

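### PFS runs to date of last contact, as OS does, so the Kaplan-Meier PFS in 14.3 can be biased upward for patients whose scans stop without documented progression

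*Combined protocol and SAP*

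**What the plan says.** Section 8.1.4 measures PFS from start of treatment "to the time of progression, death, or date of last contact; those lost to follow-up will be censored". The OS definition beside it uses the same stopping date: "Overall Survival is defined as the duration of time from the start of treatment to date of death or date of last contact". Section 5.2.1 repeats the OS rule.

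Section 14.3 states the use: "Progression-free survival and overall survival times will be displayed using Kaplan-Meier curves", with medians and confidence intervals. It adds no censoring rule. No section censors PFS at the last disease assessment or says what happens after missed scans.

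On follow-up, footnote g to the study-activities table in Section 6.0 says that "disease status is monitored bimonthly via telephone contact or EMR review after treatment termination", and Section 6.4 follows patients to death for survival endpoints. Footnote g adds: "Medical record review will be performed to coincide with the bimonthly telephone call to obtain information regarding evidence and of relapse". Scans are every other cycle, and footnote d allows that "this may occur at 6 weeks ±2 weeks, 8 weeks ± 2 weeks or 12 weeks ± 2 weeks". Section 8.1.2 provides for patients who stop treatment early: "In the event that patient discontinues treatment for reasons other than progression, imaging shall continue until progression on the same schedule". Footnote f says the same. Section 8.1.3 asks that progression be documented objectively where possible, even after treatment has stopped for general deterioration.

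**The concern.** A telephone call shows that a patient is alive, which is what OS needs. It does not show that the tumour has not grown. Record review finds only progression that someone has already imaged or biopsied, and it triggers no new scan.

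The protocol foresees patients for whom contact continues after assessment has stopped. Some stop for symptomatic deterioration without objective progression (8.1.3). Some leave because they will not comply with procedures (6.5) and, as 6.4 reads, are still followed for survival. For myeloma, imaging and marrow are done only when clinically indicated (footnotes d and h), so contact can pass the last assessment with no deviation at all. Under 8.1.4 such a patient counts as progression-free to last contact, or becomes an event only at death, however long after the last scan.

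At stake is the PFS curve of a single-arm trial, where no control arm shares the bias. Section 1.0 states the trial's goal in terms of PFS. The Kaplan-Meier PFS is also the planned progression analysis that can retain the patients whom the primary analysis drops.

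**Working it through.** **1. The plan's own figure, and whether this point reaches it.** The plan gives no precision or power figure for Kaplan-Meier PFS. Its sample size is for the primary ratio. Inputs from 14.4: difference 1.3 − 1.0 = 0.3, SD 1.71, two-sided alpha 0.05, power 80%, Wilcoxon test under normality, 20% non-evaluable.

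- Normal approximation: (1.71 × (1.960 + 0.842) / 0.3)² ≈ 255. The exact one-sample t-test needs 257.
- Wilcoxon: 257 × π/3 = 269.1, against 269 stated.
- Inflation: 269 / 0.8 = 336.25, rounded up to 337, as stated.

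The figures reproduce. Sections 5.1.1, 8.1.4 and 14.2 build the ratio from times of progression and make deaths before progression and losses non-evaluable. The last-contact rule does not enter.

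**2. Illustration of the bias.** The documents supply only the scan intervals. Everything else here is assumed: exponential time to progression (median 3 months), exponential survival after progression (median 6 months), scans every 8 weeks (1.84 months), cutoff at 24 months, and 200,000 simulated patients. A share of 10%, 20% or 30% is assigned to stop scanning at 0.5–3 months while vital status stays known. After removing those who already had an event, about 8%, 17% and 25% are effectively unscanned.

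Checks by hand:

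- With complete scanning, the last scan before 6 months is at 3 × 1.84 = 5.52 months, so 6-month PFS is about 2^(−5.52/3) = 0.28.
- The curve is 2^(−1.84/3) = 0.65 after the first scan and 2^(−3.68/3) = 0.43 after the second. The observed median is therefore 3.7 months, a scan date.
- Survival at 24 months is 2 × 2^(−24/6) − 2^(−24/3) = 0.125 − 0.004 = 0.12. Most scan-stoppers (87% in the simulation) therefore die before cutoff and end as events, not as censored observations.

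| Effectively unscanned | 6-month PFS, plan | Only the censoring date moved to last scan (deaths still events) | Share of bias due to censoring date |
|---|---|---|---|
| 8% | 31.6% | 30.9% | (31.6 − 30.9)/(31.6 − 28) = 19% |
| 17% | 35.7% | 34.3% | (35.7 − 34.3)/(35.7 − 28) = 18% |
| 25% | 39.3% | 37.5% | (39.3 − 37.5)/(39.3 − 28) = 16% |

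Repeat runs gave 31–32%, 34–36% and 38–40% under the plan. The median stays at 3.7 months at 8% and 17%. At 25% it moves to between 4.6 and 5.2 months, depending on the run.

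**3. Other ways of treating the scan-stoppers.** Censoring all of them at the last scan, whatever follows, gives about 28% throughout. Censoring a death only after two or more missed assessments gives 27.4%, 27.2% and 26.4%, slightly below the complete-scanning value. Both results assume that stopping scans is unrelated to progression.

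**4. A second set of assumptions.** N = 337, scans stopping after 0–2 assessments in 5–30% of patients, contact for 4–12 months after the last scan, survival after progression as before. With a true median time to progression of 4 months, 6-month PFS rises from about 0.38 to 0.39–0.46 and the median by about 0.1 to 0.6 months. With a true median of 2.5 months, 6-month PFS rises from about 0.21 to 0.22–0.30 and the median hardly moves.

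**The case against.** The strongest reply is that the protocol already guards against this. Imaging is to continue until progression after treatment stops for other reasons, progression is to be documented even after deterioration, and follow-up contacts cover disease status with record review. Bias needs both a departure from scanning and a progression that this follow-up misses. That stands as a limit on size. It does not settle the point, because a scan schedule is not a censoring rule and says nothing about which date applies once scans stop.

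Three stronger readings are tempting, and the documents do not support them.

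- A reader might infer that the primary endpoint is inflated too, since 2.1.1 words the ratio in terms of PFS times. The operative definitions in 5.1.1, 8.1.4 and 14.2 use times of progression and exclude deaths and losses.
- A reader might attribute the whole rise in 6-month PFS to the censoring date. Most of it comes from counting a late death as the event after missed scans. That follows from the ordinary definition of PFS as progression or death and is a separate choice.
- A reader might infer a large shift in the median, which is what 14.3 reports. In the first illustration it moves only at about 25% stopping.

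It is also fair that PFS in its own right is not among the objectives in 2.2 or the outcomes in 5.2, and that no test or decision rests on it.

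**Conclusion.** The point holds for the Kaplan-Meier PFS in 14.3 and no further. Last contact is the wrong censoring date for PFS, and the direction of bias is upward. Under the assumed 8–25% stopping scans, 6-month PFS rises from about 28% to 32–40%. About one sixth to one fifth of that rise is due to the censoring date, and the rest to deaths counted after missed scans. The documents give no rate of scan stopping, no progression rate and no survival after progression, so these figures illustrate the mechanism and do not predict this trial. If patients are scanned as 8.1.2 intends, the effect will be small. The primary ratio, 269 and 337 are unaffected. It is a moderate point about a descriptive analysis, and worth correcting because the change is short.

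**What to change.** In 8.1.4, keep date of last contact for OS only. For PFS, state that patients alive without documented progression are censored at the last adequate disease assessment by the criteria for their disease, or at treatment start if there is none after baseline.

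The censoring date alone removes only a small part of the bias, so 8.1.4 should also pre-specify how progression or death after missed assessments is handled. Report PFS both with such deaths as events and with them censored at the last adequate assessment. Neither version is safe alone. The first credits unobserved time, and the second is itself biased if patients stop scanning because they are declining. A rule triggered by a number of missed assessments is possible, but it needs a definition of a scheduled assessment for leukemia and myeloma, where imaging is not on a fixed schedule.

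The cost is a few sentences, with no new visits and no change in sample size. There will be slightly more censoring and a somewhat less favourable PFS. Assessment dates must be recorded for each disease type. Section 11.0 lists a best overall response form but no form for each assessment, and Section 8.0 leaves the response forms to an appendix still to be determined, so this should be confirmed.
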